Official Title: Immunologic response to influenza vaccination

ClinicalTrials.gov ID (NCT number): NCT03614975

Protocol Date: September 20, 2018

Scientific Background:

The Advisory Committee on Immunization Practice (ACIP) sets civilian immunization policy for the United States. In adults, cell-based recombinant vaccine has been shown to work better immunologically against the H3 strain due to lack of egg-based adaptations; however, it is not licensed for use in children. All of the published efficacy trial data on Flucelvax, the cell-based influenza vaccine approved by the FDA in 2012, were conducted when it was based on the egg-adapted strain; it first used the cell-based strain in the Fall of 2017 so effectiveness data have not been published on this update. Egg-based vaccine has only worked reasonably well against the H3 in preliminary effectiveness data for younger children; it did not work well against H3 in adult recipients due to egg-based adaptations. This study would be among the first head-to-head comparison of the current versions of these two different licensed influenza vaccines to compare the differences in antibody response among children/teens/young adults. Given recent changes in the formulation of Flucelvax and the lack of published data on this new formulation, reasonable equipoise can be assumed among these vaccines.

Influenza is a major public health burden, each year causing millions of illnesses and outpatient visits and tens of thousands of hospitalizations and deaths in the U.S. The primary influenza prevention method is vaccination; however, influenza vaccine effectiveness (VE) is variable. Host factors (e.g., age and antibody landscape), environment (e.g., tobacco exposure), virus and vaccine characteristics, such as the match between the vaccine and circulating strains, contribute to VE. This project will quantify pre- and post influenza immune response to different influenza vaccine types licensed for use (e.g., egg-based, egg-free).

Study Objectives:

Using a RCT for children 4-20 years of age, two influenza vaccines will be assessed for their immunogenic outcomes: Flucelvax (egg-free inactivated flu shot) and Fluzone (egg-based inactivated flu shot).

The study objectives are to determine the serologic, proteomic and/or peripheral blood mononuclear cells (PBMCs)/RNA responses to:

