Blood draws will be done at UPMC or Children's clinical recruitment practices. All participants will have a blood draw at baseline (may be during summer before vaccination) and at two subsequent follow-up visits. Total blood volume drawn across the study visits is ~90 mL (~30 mL drawn at each study visit). If not enough blood is obtained during study visit we will ask participants to return for an additional blood draw(s) in order to obtain the volume needed for analysis in the same study visit window; total volume for re-draws dependent upon tube type needed to fill (e.g, CPT tube for PBMCs, paxgene tube for RNA, serum tube for HI). Addendum consents for blood re-draws will be signed prior to drawing blood.

All blood samples will be collected by trained personnel with experience drawing blood from children. The blood samples will be collected using Vacutainer tubes, with uniformly colored tops according to type of processing and appropriately labeled with a uniform scheme (including study ID and collection time point). To support better understanding of the immune response following influenza vaccination, specimens will be banked for future studies that might involve proteomics, immunology, transcriptomics, or genomics. Collection of survey data done at UPMC clinical recruitment practices. Survey data will be collected from all enrolled participants at the baseline visit. If participant time constraints limits collection of the survey at the baseline visit, this information will be collected at a subsequent study visit.

Cells will be prepared and frozen according to current protocols. Plasma and cells will be stored at -80C until all specimens are collected. They will be inventoried and maintained in a database in the laboratory. Upon completion of sample collection (pre-vacc, and postvacc) samples will be sent to the funder and other contracted laboratories for further analysis. Peptoid and other laboratory testing will be conducted per current protocols.

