Specific to East Liberty Family Health Center (ELFHC) clinical recruitment site: ELFHC clinical staff's (e.g., MA/RN) activities will be limited to 1) helping to identify potential subjects, drawing blood on and providing influenza vaccination to consented and enrolled participants. Pitt research staff along with the specified MD will conduct the informed consent process with parents and children/teens and/or adult (18-20 years) participants and Pitt research staff will administer the survey at this site. Prior to staffing ELFHC for study recruitment, ELFHC helping with this research project will complete the Community Partner Research Education and Training (CPRET) prior to engagement in research activities. This training will be conducted by the Principal Investigator.

All participants will have a blood draw at baseline and at two subsequent follow-up visits. Total blood volume drawn across the study visits is ~90 mL (~30 mL drawn at each study visit: baseline, 2nd study visit, 3rd study visit). If another blood draw visit needs to be scheduled due to lack of volume collected at the prior visit (e.g., unable to collect total per visit mLs due to participant dehydration) or due to poor recovery of PBMCs, then additional blood will be collected dependent upon the type of tube needed. In some circumstances (e.g., inadequate vacuum draw/clotting issue/observed hemolysis), up to an extra tube (e.g., up through 10mL) may be drawn at any particular visit. Research staff Phlebotomists are fully trained in phlebotomy with appropriate clinical phlebotomy experience (e.g., experience with drawing blood on children). Clinical site/hospital lab Phlebotomists are fully trained and employed by UPMC. ELFHC clinical staff are fully trained in phlebotomy and vaccination.

Specific endpoints that will result in withdrawal from the study include non-compliance with allotted windows for visits in study protocol. Baseline blood draw and 2 return blood-draw visits: day 7 (range 6-9 days) and day 21 (range 21-35 days). Acceptability of samples with minor deviations from these windows will be determined by the research team on a case-by-case basis. Persons who do not meet these criteria will be dropped from the study. Onset of a new severe bleeding disorder that precludes further phlebotomy. If a participant misses day 7 but can still make the day 21 visit, they may be retained.

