As an initial step in the data analysis, descriptive statistics will be generated for each of the variables of interest, including their distributional properties. Through analyses of these distributional property assessments and relevant statistical tests, the necessary assumptions for the planned statistical tests will be investigated. If the assumptions are not met for any planned statistical test, then either the data will be transformed or a nonparametric alternative will be used.

For the analysis of the survey data, methods appropriate for the analysis of counts and proportions, depending on the specific question will be used. Due to the distributional shape in geometric mean titers (GMT), either nonparametric tests or transformation of the data will be needed; log transformation will be used for the primary endpoint. The analysis will be conducted with transformed data. The natural log of the

GMT will be the dependent variable to normalize the distribution. The mean and standard deviation of log titers will be calculated. Exact tests will be used where needed for small cell sizes. Regression models will also be used for predictors of immunogenic outcomes.

Power calculations show the need to enroll 40 per vaccine arm with 74 per vaccine arm preferred for publication; we have noted 90 enrolled per arm to account for possible attrition. A one-sided, two-sample t-test with group sample sizes of 40 and 40 achieves 98% power to detect a ratio of 2.0 when the ratio under the null hypothesis is 1.0. The coefficient of variation on the original scale is 1.0. The significance level (alpha) is 0.050. A one-sided, two-sample t-test with group sample sizes of 74 and 74 achieves 80% power to detect a ratio of 2.0 when the ratio under the null hypothesis is 1.0. The coefficient of variation on the original scale is 4.0. The significance level (alpha) is 0.050.

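### No sentence brings baseline titre into the comparison of the arms, although every participant is to have a baseline sample; adjusting for it would sharpen the comparison at almost no cost.

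*Combined protocol and SAP*

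**What the plan says.** Statistical Considerations sets the outcome scale: the natural log of the "GMT will be the dependent variable to normalize the distribution". I read this as the log of each participant's titre, since the same paragraph speaks of the mean and standard deviation of log titres. No time point, baseline covariate, fold-rise or change from baseline is given.

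The only specific between-arm test is in the two power statements: "A one-sided, two-sample t-test with group sample sizes of 40 and 40 achieves 98% power to detect a ratio of 2.0" (coefficient of variation 1.0) and "A one-sided, two-sample t-test with group sample sizes of 74 and 74 achieves 80% power to detect a ratio of 2.0" (coefficient of variation 4.0). The one sentence on modelling is "Regression models will also be used for predictors of immunogenic outcomes"; it lists no covariates and is not tied to the comparison of arms.

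Baseline data are nevertheless part of the design. Study Design and Methods says "All participants will have a blood draw at baseline (may be during summer before vaccination) and at two subsequent follow-up visits" and, on sample handling, "Upon completion of sample collection (pre-vacc, and postvacc) samples will be sent to the funder and other contracted laboratories for further analysis". Scientific Background says "This project will quantify pre- and post influenza immune response to different influenza vaccine types licensed for use".

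**The concern.** A participant's pre-vaccination titre may well predict the post-vaccination titre. If it does and the analysis ignores it, that explained variation stays in the error term and the interval for the titre ratio is wider than it need be.

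Validity is not at stake. Under randomisation the unadjusted test keeps its type I error, and its confidence interval already allows for chance baseline differences. What is at stake is precision, together with pre-specification: the trial is not blinded, and a plan that is silent on baseline leaves the choice between adjusted and unadjusted results open until the data are in hand.

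**Working it through.** **Inputs from Statistical Considerations:** ratio 2.0 against a null of 1.0; one-sided alpha 0.05; coefficient of variation (CV) 1.0 with 40 per arm and 4.0 with 74 per arm; 90 per arm enrolled. **Assumed:** r, the correlation of baseline with post-vaccination log titre. The CV is first read as that of a post-vaccination titre.

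**Step 1: the plan's own figures.** SD of ln titre = √ln(1 + CV²).
- CV 4.0: √ln 17 = 1.683. Standard error of the difference = 1.683 × √(2/74) = 0.277. Non-centrality = ln 2 / 0.277 = 0.693 / 0.277 = 2.50. The non-central t with 146 df gives 80.2% (stated 80%).
- CV 1.0: √ln 2 = 0.833. With 40 per arm, power is 98.0% (stated 98%).

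Both figures reproduce as t-tests with no baseline term.

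**Step 2: adjust for ln baseline titre.** Residual SD = SD × √(1 − r²), with 2n − 3 df. For CV 4.0 and 74 per arm:

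| r | Power | CI width relative to unadjusted | 95% CI if observed ratio is 2.0 | n per arm for 80% power |
|---|---|---|---|---|
| unadjusted | 80.2% | 1 | 1.16 to 3.46 | 74 |
| 0.2 | 81.6% | 0.980 | 1.17 to 3.42 | 71 |
| 0.3 | 83.4% | 0.954 | 1.19 to 3.37 | 68 |
| 0.5 | 89.1% | 0.866 | 1.25 to 3.21 | 56 |
| 0.7 | 96.8% | 0.714 | 1.35 to 2.96 | 38 |

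At r = 0 adjusted power is 80.2%, and at r = 0.1 it is 80.5%, so the lost degree of freedom costs nothing measurable. A simulation of this scenario (20,000 runs) gave adjusted power of 81.4%, 83.0%, 88.9% and 96.8% for the four values of r. Type I error (10,000 runs) was 4.6% to 5.2% for both methods.

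**Step 3: other settings, r = 0.2, 0.3, 0.5, 0.7.**
- CV 4.0, 90 per arm, no attrition: 86.6% unadjusted; 87.8%, 89.3%, 93.7%, 98.6% adjusted.
- CV 1.0, 40 per arm: 98.0% unadjusted; 98.3%, 98.7%, 99.6%, 99.98% adjusted.

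**Step 4: if the ratio of 2.0 is a ratio of fold-rises.** The stated CV is then that of the change, and the t-test is a change-score test. With equal baseline and post-vaccination variances, adjustment has residual SD = SD × √((1 + r)/2). For CV 4.0 and 74 per arm, 80.2% becomes 94.2%, 92.6%, 89.1% or 85.5% for r = 0.2, 0.3, 0.5 or 0.7. Adjustment is no worse under either reading.

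**Step 5: why not a plain change score.** Returning to the post-vaccination reading with equal variances, its SD is SD × √(2(1 − r)). Power with 74 per arm is 62.8%, 67.8%, 80.2% and 94.2% for r = 0.2, 0.3, 0.5 and 0.7. It is no better than the unadjusted test unless r exceeds 0.5, and it is below the adjusted model at each of these values.

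**Step 6: missing baseline titres.** Suppose 10% lack one (assumed). Dropping them leaves 67 per arm and 78.1% power at r = 0.2, below the 80.2% of the unadjusted test. Keeping them, with the overall mean plus a missing-value indicator, gives 81.0% by simulation.

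**The case against.** The strongest reply is that no error is shown. The t-test appears only as a sizing device; sizing on an unadjusted test is conservative and compatible with an adjusted analysis later; and the regression sentence has room for a baseline covariate. All of this is true. The plan does not commit itself to an unadjusted analysis; it fails to say which analysis will be done. That is still a gap, because nothing names baseline titre or ties regression to the arms.

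Second, the size rests on an r that the documents do not give, and on the less favourable CV. This also stands. At CV 4.0 with 74 per arm, r of 0.3 or less adds at most 83.4 − 80.2 = 3.2 points. A baseline draw taken in the summer before vaccination could lower r. At CV 1.0 the unadjusted power is already 99.97% with 74 per arm, so only the interval benefits. None of this gives a reason to leave baseline out, since adjustment costs nothing measurable even at r = 0.

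Third, the ratio could be one of fold-rises, so that baseline would already be in the outcome. No text says so, and Step 4 shows that adjustment still helps in that case.

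Fourth, a baseline titre assay is inferred rather than stated outright. That is fair, but pre-vaccination samples are to be sent for analysis, and the stated aim is to quantify response before and after vaccination.

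Lastly, the 10% missing rate has no source, and every participant is meant to have a baseline draw. The figure is only an illustration. The protocol does foresee draws that fall short in volume, so a rule for missing values is prudent.

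**Conclusion.** The concern holds as an avoidable loss of precision and a gap in pre-specification. It is not a validity failure, and the sample size is correct for the test it names. At CV 4.0 with 74 per arm the gain runs from about 1 point of power (r = 0.2) to about 17 points (r = 0.7). At CV 1.0 with 40 per arm it is at most 2 points. These figures assume log-normal titres and a value of r that the documents do not supply, so confidence in the size of the gain is only moderate. The recommendation itself does not depend on r. It should be made, but the trial does not stand or fall by it.

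**What to change.** State in Statistical Considerations that the arms are compared with a linear model of ln post-vaccination titre on randomised arm, with the same strain's ln baseline titre as covariate. Report the adjusted titre ratio with its 95% confidence interval, and keep the unadjusted t-test as a sensitivity analysis. Because the sizing test is one-sided at 0.05, also say which sidedness the adjusted test uses.

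Keep participants whose baseline titre is missing, for example with the overall mean plus a missing-value indicator. Do not substitute a plain change score. Age and prior-season vaccination may be added as covariates, though no gain is claimed for them here.

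The primary strain, the primary visit and the multiplicity rule also need to be fixed, but that is a separate point, and this change does not make every strain a primary test.

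The cost is wording in the statistical section. Baseline draws are already planned for all, and pre-vaccination samples are already to be sent for analysis; no extra participants, visits or blood are needed.

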The PI and co-investigators will monitor the progress of the research study, including assessments of data quality and timeliness and participant recruitment, accrual and retention, subject's confidentiality, any adverse event data, unanticipated problems and external factors or relevant information that might have an impact on the safety or ethics of the study. The PI and co-investigators will meet on a regular basis to discuss these

issues. Minutes will be recorded for each of the meetings which will occur on a bimonthly to quarterly basis, depending on the stage of the study. At the time of the IRB renewal the PI will submit in writing to the IRB a summary report of the data and safety monitoring activities from the past year. The CDC and University of Pittsburgh will hold phone calls at least quarterly to address the progress of the research study, including assessments of data quality and timeliness and participant recruitment, accrual and retention, subject's confidentiality, any adverse event data, unanticipated problems and external factors or relevant information that might have an impact on the safety or ethics of the study. Minutes will be recorded for each of the meetings. Adverse events will be reported to the HRPO per its Policies and Procedures Manual.

Eligibility Criteria:

Inclusion Criteria:

1. Males and females aged 4-20 years whose prior vaccination history is available (which can be determined based on the medical record or state registry for the prior year or participation in our previous studies of childhood influenza vaccine (previous participants are a high priority for enrollment);
2. Planning to receive seasonal influenza vaccination at one of our recruiting sites
3. \geq 37 pounds

Exclusion Criteria:

1. Unable or unwilling to complete all required study activities, including informed consent and bloodwork
2. Already received the influenza vaccine for the current year
3. Have a known immunocompromising condition or on an immunosuppressing medication (e.g., high dose steroids)
4. Known to be pregnant
5. Have a history of severe allergy to eggs or to influenza vaccine or any of its components

Statistical Considerations:

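### The only between-arm comparison named is an unadjusted two-sample t-test; prespecifying age and baseline log titre as covariates would gain some precision at almost no cost

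*Combined protocol and SAP*

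**What the plan says.** The analysis text under Statistical Considerations says that "log transformation will be used for the primary endpoint" and that the natural log of the "GMT will be the dependent variable to normalize the distribution". It names no primary test or model for comparing the arms. The two-sample t-test appears only in the power paragraph, once for 40 per arm ("A one-sided, two-sample t-test with group sample sizes of 40 and 40 achieves 98% power to detect a ratio of 2.0") and once for 74 per arm ("A one-sided, two-sample t-test with group sample sizes of 74 and 74 achieves 80% power to detect a ratio of 2.0"). Neither statement includes a covariate.

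Regression does appear: "Regression models will also be used for predictors of immunogenic outcomes". That sentence lists no predictors and does not say that vaccine arm is in the model.

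Elsewhere, Scientific Background lists "Host factors (e.g., age and antibody landscape") among the contributors to vaccine effectiveness, and says of H3: "Egg-based vaccine has only worked reasonably well against the H3 in preliminary effectiveness data for younger children". The first inclusion criterion is "Males and females aged 4-20 years whose prior vaccination history is available", so age is known for everyone enrolled. Study Design and Methods plans a baseline blood draw for every participant and 1:1 computer-generated allocation, with no stratification by age mentioned.

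**The concern.** The age range is wide, and the background section itself points to age and prior antibody as host factors. In an unadjusted comparison, any log-titre variance that these explain remains in the error term. The interval for the ratio of geometric mean titres (GMT) is then wider than it need be, and power is lower.

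This matters most at CV 4.0, the scenario behind the preferred 74 per arm, where power is 80% with no slack. There is also a point of discipline. The trial is not blinded and the regression predictors are left open, so an adjustment chosen late could be chosen with titres by arm in view.

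**Working it through.** **Inputs from Statistical Considerations.** GMT ratio 2.0 against a null of 1.0; one-sided alpha 0.05; CV 1.0 with 40 per arm and CV 4.0 with 74 per arm; 90 enrolled per arm.

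**Assumed input.** R² is the within-arm share of log-titre variance explained by the baseline covariates together. The documents do not give it; 2%, 5%, 10% and 20% are used.

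**Step 1: log scale.** The difference is ln 2 = 0.693. The SD is σ = √ln(1 + CV²):
- CV 1.0: √ln 2 = 0.833
- CV 4.0: √ln 17 = 1.683

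**Step 2: reproduce the plan.** The standard error is σ√(2/n), with power from the noncentral t on 2n − 2 degrees of freedom.
- 40 per arm, CV 1.0: SE = 0.833 × √(2/40) = 0.186; noncentrality 0.693/0.186 = 3.72; power 98.0% (plan: 98%).
- 74 per arm, CV 4.0: SE = 1.683 × √(2/74) = 0.277; noncentrality 0.693/0.277 = 2.50; power 80.2% (plan: 80%).

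Both figures stand. Two-sided versions give 95.7% and 70.1%, so the plan's figures are indeed one-sided.

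**Step 3: adjust.** Replace σ by σ√(1 − R²) and take one degree of freedom per covariate. One covariate (2n − 3) and two covariates (2n − 4) agree to within 0.1 percentage point of power. The 95% interval is the ratio multiplied and divided by exp[t(0.975) × σ√(1 − R²) × √(2/74)].

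| R² (assumed) | σ√(1 − R²), CV 4.0 | Power, 74/arm, CV 4.0 | Power, 90/arm, CV 4.0 | n/arm to match 80.2% | 95% CI factor, 74/arm, CV 4.0 | Power, 40/arm, CV 1.0 |
|---|---|---|---|---|---|---|
| unadjusted | 1.683 | 80.2% | 86.6% | 74 | 1.73 | 98.0% |
| 2% | 1.666 | 80.9% | 87.2% | 73 | 1.72 | 98.1% |
| 5% | 1.641 | 81.9% | 88.1% | 71 | 1.70 | 98.4% |
| 10% | 1.597 | 83.7% | 89.5% | 67 | 1.68 | 98.8% |
| 20% | 1.505 | 87.3% | 92.4% | 60 | 1.63 | 99.3% |

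**Step 4: the downside.** With R² = 0 the formula leaves power at 80.2%.

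The formula ignores chance imbalance in the covariate. A simulation covers that: 20,000 replicates, age as the single covariate drawn evenly from 4 to 20, 74 per arm, CV 4.0. It gave adjusted power of 80.5%, 81.7%, 83.6% and 86.6% for R² of 0, 5%, 10% and 20%, against 80.7%, 80.2%, 80.4% and 79.9% unadjusted (simulation SE 0.3 points). Adjusted type I error was 4.9% to 5.3% (SE 0.15 points).

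**The case against.** The strongest reply is that the t-test is a basis for sizing, not a declared primary analysis. Sizing on a simple test is a conservative convention, and a regression containing arm and age would fit the analysis text. This stands in part. A reader might infer that the plan commits itself to an unadjusted primary analysis, or that covariate analysis is absent; the documents support neither. What they do show is that no adjusted between-arm model is prespecified and no covariate is named.

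A second reply is that the gain rests on an R² the documents do not supply. The background links host factors to vaccine effectiveness, not to variance in log titre. This also stands. At R² of 5% or less the gain at 74 per arm is under 2 points.

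Third, the gain matters only at the pessimistic end of the CV range. At 74 per arm, unadjusted power is already 99.97% at CV 1.0 and 95.2% at an assumed CV of 2.0. At 90 per arm without attrition it is 86.6% even at CV 4.0. Uncertainty about the CV therefore matters more than the adjustment.

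Fourth, adjusting for age alone would use only half of what the background names. Antibody landscape is listed beside age, and baseline blood is planned for everyone, so baseline log titre belongs in the same model.

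The background's contrast between younger children and adults on H3 might also suggest a vaccine-by-age interaction. It is not worth adding. At 74 per arm and CV 4.0 its two-sided power is 24% for ratios of 2.0 versus 1.0 in two equal age halves, and 8% for 2.0 versus 1.5. With age continuous, and the log ratio linear between the same end values, it is 12% and 6%.

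**Conclusion.** The point holds as a modest opportunity to gain precision, not as an error. A reader might infer that the pooled ratio is biased without age adjustment, or that the trial is undersized. Neither follows: allocation is randomised, so the unadjusted comparison is valid, and both stated powers reproduce.

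At CV 4.0 and 74 per arm the benefit is 0.7 to 7.1 power points over R² of 2% to 20%, with a confidence interval on the log scale about 1% to 11% narrower. At CV 1.0 it is negligible. These figures assume log-normal titres, covariates linear on the log scale, and an R² that has to be taken as a range. The benefit of fixing the covariates in advance does not depend on R².

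**What to change.** Add one statement to Statistical Considerations before titres are examined by arm. The pooled GMT ratio will be estimated, with its confidence interval, from a linear model of log post-vaccination titre on vaccine arm, with age (continuous) and baseline log titre as covariates. Keep the unadjusted t-test as the conservative basis for sample size; the power statements need no change. Leave out a vaccine-by-age interaction.

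The cost is two degrees of freedom and a sentence or two of text. Age is already required for eligibility and the baseline draw is already planned, so no participants, visits or blood samples are added. If the sponsor separately lists the predictors for the planned regression models, this statement can sit in the same paragraph.
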